FULL/LONG TITLE OF THE STUDY

EFFECTIVENESS OF PRE-OPERATIVE CARDIOPULMONARY EXERCISE TESTING IN PREDICTING POST-OPERATIVE MORBIDITY AND MORTALITY AFTER PANCREATODUODENECTOMY – A RETROSPECTIVE COHORT STUDY

SHORT STUDY TITLE / ACRONYM

THE ROLE OF PRE-OPERATIVE CPET IN PANCREATODUODENECTOMY

RESEARCH REFERENCE NUMBERS

IRAS Number: 284565

SPONSORS Number: NONE

FUNDERS Number: NONE

Document submitted to HRA/IRAS Date: 11-12-2020

Amendments:

Document amended on 21-09-2023 for submission to Clinicaltrials.gov

Document amended again on **28-09-2023** for submission to Clinicaltrials.gov

STUDY SUMMARY

Study Title	EFFECTIVENESS OF PRE-OPERATIVE CARDIOPULMONARY EXERCISE TESTING IN PREDICTING POST-OPERATIVE MORBIDITY AND MORTALITY AFTER PANCREATODUODENECTOMY – A RETROSPECTIVE COHORT STUDY
Internal ref. no. (or short title)	THE ROLE OF PRE-OPERATIVE CPET IN PANCREATODUODENECTOMY
Study Design	RETROSPECTIVE ANALYSIS OF PROSPECTIVELY MAINTAINED DATABASE
Study Participants	PARTICIPANTS WHO HAVE UNDERGONE PANCREATIC RESECTIONS FROM APRIL 2016 TO MARCH 2020
Planned Size of Sample (if applicable)	Approximately 140
Follow up duration (if applicable)	90 DAYS
Planned Study Period	1 YEAR
Research Question/Aim(s)	To assess the usefulness and effectiveness of pre-operative CPET in predicting morbidity and mortality after pancreatoduodenectomy

[figure not shown]
FUNDING AND SUPPORT IN KIND

FUNDER(S) (Names and contact details of ALL organisations providing funding and/or support in kind for this study)	FINANCIAL AND NON FINANCIALSUPPORT GIVEN BY
ROYAL BLACKBURN HOSPITAL, EAST LANCASHIRE HOSPITALS NHS TRUST [name] CONTACT NUMBER: [name]	NON FINANCIAL SUPPORT

ROLE OF STUDY SPONSOR AND FUNDER:

Non-financial support for the study.

STUDY FLOW CHART:

STUDY PROTOCOL

1 BACKGROUND:

Pancreatic resections, particularly Pancreatoduodenectomy, for tumors in the pancreas head, is considered the standard modality of management for pancreatic and periampullary tumors. The morbidity and mortality associated with the procedure, has improved in the recent times, but it still remains high. Post-operative pancreatic fistula, in particular, has an incidence ranging from 20-25%¹. The operability of the tumour not only depends on the initial staging of the tumour, but also on physiological status of the patient, fitness, pre-existing comorbidities and age. The use of cardiopulmonary Exercise Testing (CPET), in assessing physiological status of the patient has been in discussion, in the past two decades. The efficacy and use of CPET as a guide for pre-operative optimisation of the patient undergoing major abdominal surgeries, has been proven². Levett D Z H et al. in 2017, provided Level 1 evidence, supporting the same and also drew guidelines for the clinicians for indications and interpretation of CPET for perioperative participants².

Chandrabalan V V et al. in 2013, conducted a retrospective study, which showed that CPET is useful to predict occurrence of post-operative pancreatic fistula, intra-abdominal abscess and post-operative length of hospital stay³. Junejo MA et al. in 2014, by a prospective study showed that, CPET can be used as an adjunct to predict post-operative outcomes in pancreatoduodenectomy. This study showed that raised VE/VCO₂ in CPET could predict early post-operative death⁴.

[figure not shown]
REFERENCES:

2. Levett D Z H, Jack S, Swart M et al. (2018). Perioperative cardiopulmonary exercise testing (CPET): consensus clinical guidelines on indications, organization, conduct, and physiological interpretation. *British Journal of Anaesthesia*,120(3):484-500.

2 RATIONALE:

With the above mentioned background, we aim to do a retrospective analysis of participants who have undergone pancreatic resections, at our centre. The aim is to assess the ability of physiological parameters assessed by CPET, in predicting post-operative morbidity and mortality. This study also aims at evaluating and analysing a comparator group of participants who did not have CPET and assess their perioperative outcomes, in particular post-operative complications, with those who had CPET.

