3 THEORETICAL FRAMEWORK

4 RESEARCH QUESTION/AIM(S)

Objectives: To assess if pre-operative cardiopulmonary exercise testing is useful and effective in predicting at risk participants for post-operative morbidity and mortality, who undergo Whipple's surgery.

DATA ELEMENTS

1. Participant flow

Recruitment Details:

Participants for the study will be identified from a prospectively maintained database, by database search from April 2016 to March 2020, online records, clinical portal and Somerset cancer registry. Duplicates will be removed, cases will be screened.

This is a single centre study, to be done at, Royal Blackburn Hospital, East Lancashire Hospitals NHS trust, a District general Hospital in North of England. The study will be carried out in the department of General and HPB surgery, in liaison with Department of anaesthesia. This is the HPB referral centre for Lancashire and South Cumbria and incorporates participants referred for pancreatic surgery from three hospital trusts (Lancashire Teaching, University Hospital Morecambe Bay and Blackpool Teaching Hospitals).

Arm/Group Information:

The study will have two groups of participants, one who have undergone CPET pre-operatively and the other who have not undergone CPET.

Group 1 – Participants who have undergone CPET as a part of pre-operative assessment as well as P-POSSUM score calculation for predicting post-operative morbidity and mortality.

P-POSSUM is a scoring system for general elective and emergency surgeries which takes into account various physiological and operative parameters to calculate risk of morbidity and mortality in terms of percentages.

Group 2 – Participants who have not undergone CPET as a part of pre-operative assessment rather have only P-POSSUM calculated for predicting post-operative morbidity and mortality.

Period of Overall Study:

The study was conducted from February 2021 to March 2022. The database search was conducted and data collated. The study was conducted in one stage over a year.

Participants:

143 participants were recruited for the study during a period of 1 year. Out of 143 participants, 30 participants had undergone CPET as a part of pre-operative assessment.

2. Baseline Characteristics:

Baseline Analysis Population Information:

Data on baseline characteristics included age, sex, comorbidities, Rockwell frailty score, ASA grade, BMI.

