Data on study specific characteristics included dates of admission and discharge, diagnosis, details of surgery undergone, details of morbidity using Clavien-Dindo classification and mortality. Details of CPET and its measures as well as P-POSSUM scores were collated.

CPET specific data collected:

- 1) Exercise induced ST ischaemia- yes/no
- 2) VO₂ peak: actual and predicted
- 3) Anaerobic threshold:
- 4) VE/VCO₂:
- 5) Pulmonary function test- normal/ obstructive/ restrictive
- 6) Duration of pedalling bike
- 7) 30 day predicted risk

3. Outcome Measures:

Primary Outcome measures:

Primary outcome was measured in terms of CPET/P-POSSUM predicted mortality compared to actual 30 day mortality.

- In-hospital mortality
- 30 days
- 90 days

Secondary outcome measures:

Secondary outcome was measured in terms of CPET/ P-POSSUM predicted morbidity compared to actual morbidity (Clavien-Dindo grade 3 and above).

Morbidity in terms of:

- Post-operative pancreatic fistula
- Biliary fistula
- Delayed gastric emptying
- Bleeding
- Intra-abdominal collection
- Renal failure
- Cardiac complications
- Pulmonary complications
- Pulmonary embolism /DVT

The occurrence of morbidity and mortality were measured in terms of numbers and percentages. The calculated risk of morbidity and mortality by CPET and P-POSSUM are in terms of percentages, ranging from 0 to 100%, higher the percentage leading to worse outcome.

Statistical analyses overview:

The baseline characteristics were analysed using percentages and frequencies (mean, median, mode, standard deviation). Chi-square test was used to assess if the two study groups were

comparable. The p-value calculated was considered significant if <0.05 and confidence interval of 95%.

The study specific measures were analysed using parametric and non-parametric tests and binary logistic regression analyses to compare predicted to actual mortality and morbidity, between the participants who have had CPET and those who have not.

Univariate and multivariate analysis were done to assess if CPET measures could be used to predict occurrence of post-operative complications and morbidity.

4. Adverse Event information:

This was a retrospective review of a prospectively maintained database.

No adverse events were overcome during the time of the study

5. Limitations and Caveat:

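### The comparison of complications between CPET and no-CPET participants gives date of surgery no role over a four-year window, which leaves an unchecked, though not demonstrated, risk of bias.

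*Combined protocol and SAP*

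**What the plan says.** - The Study Summary takes participants operated on "FROM APRIL 2016 TO MARCH 2020". The recruitment details in section 4 repeat that window for the database search.
- Section 2 (Rationale) states, as a further aim, "evaluating and analysing a comparator group of participants who did not have CPET and assess their perioperative outcomes, in particular post-operative complications", compared with those who had CPET.
- Section 4 (Participants) gives 143 participants, of whom 30 had CPET.
- The baseline characteristics listed are age, sex, comorbidities, frailty score, ASA grade and BMI. A chi-square test is used to judge whether the groups are comparable.
- The statistical analyses overview names parametric and non-parametric tests and binary logistic regression "to compare predicted to actual mortality and morbidity, between the participants who have had CPET and those who have not". It names no covariates and no year term, stratum or matching.
- Calendar time could be derived: "Data on study specific characteristics included dates of admission and discharge". The analysis section gives these dates no role.
- Section 1 (Background) remarks: "The morbidity and mortality associated with the procedure, has improved in the recent times, but it still remains high". It gives no figure and no dates, and does not refer to this centre.
- Section 5 (Limitations and Caveat) mentions the small CPET group but not calendar time.

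**The concern.** CPET was not allocated by design, so the two groups may differ in when they were operated on as well as in who they are. If complications changed over the four years and CPET use changed too, each group carries the outcomes of its own years. The groups would then differ even if CPET made no difference. With falling complications, rising CPET use makes the CPET group look better and falling use makes it look worse.

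Balance on age, ASA grade or frailty does not remove this. Nor does comparison with P-POSSUM, which section 4 describes as built from physiological and operative parameters: a fixed score does not follow a drift in outcomes.

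At stake is the between-group comparison of complications, and the between-group comparison of actual with predicted outcomes.

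**Working it through.** **Inputs from the documents.** 143 participants, 30 with CPET, so 143 - 30 = 113 without. Forty had an intra-abdominal collection (section 8), used here as the example complication. The significance level is 0.05; sidedness is not stated, and two-sided is assumed.

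**The document's own figures.** 30/143 = 20.98%, which matches the stated 21%. 40/143 = 27.97%; the printed 28.2% equals 40/142, which suggests one missing value and does not matter here.

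**Precision.** With p = 40/143, SE = sqrt[p(1 - p)(1/30 + 1/113)] = 0.0922, so the 95% half-width is 1.96 × 0.0922 = 0.181, or about 18 points.

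**Assumptions.** The documents give no CPET counts or complication rates by year. I assume equal numbers of operations over time, a complication rate averaging 28% that falls linearly, and no effect of CPET. Then:

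spurious difference = slope of the rate × (mean time of CPET group - mean time of no-CPET group).

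*By year (1 to 4, overall mean 2.5), with fall D from year 1 to year 4.* The slope is -D/3 per year. If CPET use rises 1:2:3:4, the CPET mean year is 3.0 and the no-CPET mean is (2.5 × 143 - 3.0 × 30)/113 = 2.367, a gap of 0.633. For D = 10 points the difference is -(10/3) × 0.633 = -2.1 points. The other patterns follow in the same way:

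| CPET use | Gap in mean year | D = 10 points | D = 20 points |
|---|---|---|---|
| Even | 0 | 0 | 0 |
| Rising 1:2:3:4 | 0.633 | -2.1 | -4.2 |
| All in last 2 years | 1.265 | -4.2 | -8.4 |
| All in last year | 1.898 | -6.3 | -12.7 |
| Falling 4:3:2:1 | -0.633 | +2.1 | +4.2 |

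By normal approximation, the false-positive rate of the unadjusted test is 5% with even use. For rising use it is 5.6% (D = 10) and 7.4% (D = 20). With all CPETs in the last year it is 10.5% and 27.9%.

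*By month (48 months), with the fall measured from first month to last.* If all CPETs fall in the last 24 months the gap in mean month is 15.19; if all fall in the last 12 it is 22.78.
- Fall from 35% to 21%: -(14/47) × 15.19 = -4.5 points, and -(14/47) × 22.78 = -6.8 points.
- Fall from 40% to 16%: -(24/47) × 15.19 = -7.8 points, and -(24/47) × 22.78 = -11.6 points. Simulated false-positive rates (4,000 cohorts each) were 12.5% and 22.6%.

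The two scales agree: a 24-point fall from first to last month is 24 × 36/47 = 18.4 points between the mean rates of the first and last years.

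**Cost of a linear time term.** On a linear approximation the interval widens by 1/sqrt(1 - r²), where r² = (30/143)(113/143) × gap² / variance of time. The variance is 1.25 for years and 191.9 for months.
- Rising 1:2:3:4: r² = 0.053, 3% wider.
- Last 24 months: r² = 0.199, 12% wider (13% with year coded 1 to 4).
- Last 12 months: r² = 0.448, 35% wider (38% with year coded 1 to 4).

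**Cost of dropping years without CPET.** A quarter of the operations is 143/4 = 35.75. If all 30 CPETs fall in the last year, 5.75 comparators remain and the half-width is 1.96 × sqrt[p(1 - p)(1/30 + 1/5.75)], or about 40 points. If they fall in the last two years, 41.5 remain and it is about 21 points.

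**The case against.** The strongest objection is that neither condition for bias is documented. The remark on improving outcomes is general background and goes on to say that the risks remain high; it does not show a trend at this centre between 2016 and 2020. No CPET counts by year are given. Both groups come from the same database, centre and window, so this is not a historical-control design. All of that stands. A reader might infer that the comparison is biased, or that the background section admits a trend in these data; the documents support neither. They do give a reason to look: section 1 dates consensus guidance on indications for perioperative CPET to 2017 (2018 in the reference list), inside the window. That makes even use something to check, and is not evidence that use changed here.

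The large figures also depend on extreme clustering. Thirty CPETs in the last 12 months would be about 84% of that year's 35.75 operations, after none in the preceding 107. The gradual pattern with a 10-point fall gives about -2 points, small beside an 18-point half-width. This stands too, although a wide interval does not correct a shifted centre.

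Finally, no covariates are named for any model, so year is omitted by silence and not by choice, and the documents do not say why a participant had CPET. That is a wider gap in the same comparison. It does not remove this one, which can be checked from data already held.

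**Conclusion.** The point holds as an unchecked risk of bias in a stated aim, not as a shown bias. Neither the described analyses nor a comparability check on the listed baseline characteristics would reveal a difference in era between the 30 and the 113.

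Its size is unknown from the documents. If volume is even, the rate falls linearly around 28% and CPET has no effect, the spurious difference runs from 0 with even use, through about -2 points (gradual rise in use, 10-point fall), to about -12 points (all CPETs in the last year, 24-point fall from first month to last). The sign reverses if CPET use fell. If use by year proves even, the concern closes.

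A reader might also infer that the reported finding for anaerobic threshold ≤ 14 is undermined. It is not directly affected: it compares participants within the CPET group, and section 8 reports no CPET versus no-CPET estimate for complications.

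**What to change.** 1. Derive year of surgery from the admission dates already held, and tabulate CPET use and complications by year.
2. Report the CPET versus no-CPET comparison of complications both unadjusted and with one linear year term in the logistic model, each with a 95% confidence interval. A single term suits the roughly 40 collection events. Treat the between-group comparison of actual with predicted outcomes in the same way.
3. Do not make exclusion of years without CPET the main analysis. Show it only as a sensitivity analysis, and only if enough concurrent comparators remain.
4. If use by year turns out uneven, add calendar time to the limitations.

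The cost is one derived variable, one table and one model term, with no new data. Almost no precision is lost if CPET use was even or changed gradually. If CPETs cluster in the last one or two years, intervals widen by roughly 10% to 35% on the linear approximation, slightly more with year coded 1 to 4. That widening reflects how little concurrent comparison such data would contain.

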3 THEORETICAL FRAMEWORK

4 RESEARCH QUESTION/AIM(S)

Objectives: To assess if pre-operative cardiopulmonary exercise testing is useful and effective in predicting at risk participants for post-operative morbidity and mortality, who undergo Whipple's surgery.

DATA ELEMENTS

1. Participant flow

Recruitment Details:

Participants for the study will be identified from a prospectively maintained database, by database search from April 2016 to March 2020, online records, clinical portal and Somerset cancer registry. Duplicates will be removed, cases will be screened.

This is a single centre study, to be done at, Royal Blackburn Hospital, East Lancashire Hospitals NHS trust, a District general Hospital in North of England. The study will be carried out in the department of General and HPB surgery, in liaison with Department of anaesthesia. This is the HPB referral centre for Lancashire and South Cumbria and incorporates participants referred for pancreatic surgery from three hospital trusts (Lancashire Teaching, University Hospital Morecambe Bay and Blackpool Teaching Hospitals).

Arm/Group Information:

The study will have two groups of participants, one who have undergone CPET pre-operatively and the other who have not undergone CPET.

Group 1 – Participants who have undergone CPET as a part of pre-operative assessment as well as P-POSSUM score calculation for predicting post-operative morbidity and mortality.

P-POSSUM is a scoring system for general elective and emergency surgeries which takes into account various physiological and operative parameters to calculate risk of morbidity and mortality in terms of percentages.

Group 2 – Participants who have not undergone CPET as a part of pre-operative assessment rather have only P-POSSUM calculated for predicting post-operative morbidity and mortality.

Period of Overall Study:

The study was conducted from February 2021 to March 2022. The database search was conducted and data collated. The study was conducted in one stage over a year.

Participants:

143 participants were recruited for the study during a period of 1 year. Out of 143 participants, 30 participants had undergone CPET as a part of pre-operative assessment.

2. Baseline Characteristics:

Baseline Analysis Population Information:

Data on baseline characteristics included age, sex, comorbidities, Rockwell frailty score, ASA grade, BMI.

Data on study specific characteristics included dates of admission and discharge, diagnosis, details of surgery undergone, details of morbidity using Clavien-Dindo classification and mortality. Details of CPET and its measures as well as P-POSSUM scores were collated.

CPET specific data collected:

- 1) Exercise induced ST ischaemia- yes/no
- 2) VO₂ peak: actual and predicted
- 3) Anaerobic threshold:
- 4) VE/VCO₂:
- 5) Pulmonary function test- normal/ obstructive/ restrictive
- 6) Duration of pedalling bike
- 7) 30 day predicted risk

3. Outcome Measures:

Primary Outcome measures:

Primary outcome was measured in terms of CPET/P-POSSUM predicted mortality compared to actual 30 day mortality.

- In-hospital mortality
- 30 days
- 90 days

Secondary outcome measures:

Secondary outcome was measured in terms of CPET/ P-POSSUM predicted morbidity compared to actual morbidity (Clavien-Dindo grade 3 and above).

Morbidity in terms of:

- Post-operative pancreatic fistula
- Biliary fistula
- Delayed gastric emptying
- Bleeding
- Intra-abdominal collection
- Renal failure
- Cardiac complications
- Pulmonary complications
- Pulmonary embolism /DVT

The occurrence of morbidity and mortality were measured in terms of numbers and percentages. The calculated risk of morbidity and mortality by CPET and P-POSSUM are in terms of percentages, ranging from 0 to 100%, higher the percentage leading to worse outcome.

Statistical analyses overview:

The baseline characteristics were analysed using percentages and frequencies (mean, median, mode, standard deviation). Chi-square test was used to assess if the two study groups were

comparable. The p-value calculated was considered significant if <0.05 and confidence interval of 95%.

The study specific measures were analysed using parametric and non-parametric tests and binary logistic regression analyses to compare predicted to actual mortality and morbidity, between the participants who have had CPET and those who have not.

Univariate and multivariate analysis were done to assess if CPET measures could be used to predict occurrence of post-operative complications and morbidity.

4. Adverse Event information:

This was a retrospective review of a prospectively maintained database.

No adverse events were overcome during the time of the study

5. Limitations and Caveat:

This was a retrospective review of a prospectively maintained database. The participants who underwent CPET was small compared to participants who did not. A prospective study with a large sample size is required to obtain more reliable results.

6. Certain Agreements:

All PIs are employees of Sponsor.

There is no specified results disclosure agreement between the PIs and sponsor.

7. Results Point of Contact

Name: Miss [name] (Principal Investigator)

Organization Name: East Lancashire Hospitals NHS Trust

[contact]

Email Id: [contact]

8. Results of the study

143 participants had Pancreatoduodenectomy during the study period. CPET was performed in 30 participants (21%). The participants' age was 67 ± 9 (Mean \pm SD). Forty participants (28.2%) had developed intra-abdominal collection (Clavien-Dindo III). In the CPET subgroup, Anaerobic Threshold (AT) ≤ 14 on CPET was a risk factor to develop intra-abdominal collection, according to univariate analysis (60% Vs 9%, p-value 0.02) and multivariate analysis (HR 3.5, 95% CI 1.6-657, p-value 0.02). Another significant risk factor was post-operative pancreatic leak (POPF) (40% Vs 22%, p-value 0.04).

By this study we concluded that participants who have Anaerobic Threshold ≤ 14 on CPET, are more likely to develop intra-abdominal collection requiring drainage after Pancreatoduodenectomy. This group of participants will be less likely to start chemotherapy early.

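### The results summary omits the stated mortality and overall morbidity comparisons and concludes, without an exploratory label, on one complication at an unexplained AT cut-off, with a ratio that does not fit its interval

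*Combined protocol and SAP*

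**What the plan says.** All references are to the combined protocol and SAP.

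- **Primary outcome (Outcome Measures).** "Primary outcome was measured in terms of CPET/P-POSSUM predicted mortality compared to actual 30 day mortality". In-hospital, 30-day and 90-day mortality are listed beneath it.
- **Secondary outcome (Outcome Measures).** "Secondary outcome was measured in terms of CPET/ P-POSSUM predicted morbidity compared to actual morbidity (Clavien-Dindo grade 3 and above"). Nine complication types follow, intra-abdominal collection among them.
- **Predicted risks.** "The calculated risk of morbidity and mortality by CPET and P-POSSUM are in terms of percentages". The CPET data list has a single risk item, "30 day predicted risk", which does not name the event predicted. Group 2 is described as "Participants who have not undergone CPET as a part of pre-operative assessment rather have only P-POSSUM calculated".
- **Analysis (Statistical analyses overview).** Binary logistic regression is named for predicted against actual mortality and morbidity, CPET v no CPET. Separately: "Univariate and multivariate analysis were done to assess if CPET measures could be used to predict occurrence of post-operative complications and morbidity". Significance is set at p below 0.05. No AT cut-off, no order among the complications and no multiplicity control is stated.
- **Results of the study.** Of 143 participants, 30 had CPET. Forty (28.2%) had an intra-abdominal collection. In the CPET subgroup, AT ≤ 14 is reported as a risk factor for collection: 60% v 9%, p = 0.02 (univariate); HR 3.5, 95% CI 1.6 to 657, p = 0.02 (multivariate). The conclusion states this association as a finding.
- **Limitations and Caveat.** The CPET group is acknowledged to be small, and "A prospective study with a large sample size is required to obtain more reliable results".

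**The concern.** The document poses a question about mortality, then one about overall serious morbidity, and its results answer a narrower one. A reader cannot learn from the summary whether CPET or P-POSSUM predicted death, or how predicted morbidity compared with observed. What the reader does get is a firm statement about one complication, from a subgroup of at most 30, at a threshold whose origin is not given. With several CPET measures and nine complications available, a single p of 0.02 means something different if it was the one association sought than if it was the best of many. The statement also leans on an estimate that cannot be right as printed. The document says it was amended for registry submission, so this wording may be what outside readers rely on.

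**Working it through.** **1. Stated outcomes against reported results**

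| Stated in Outcome Measures or analysis overview | In Results of the study |
|---|---|
| Actual 30-day mortality | No deaths given for any window |
| CPET and P-POSSUM predicted mortality | Not given |
| Overall Clavien-Dindo grade 3 or higher, actual and predicted | Not given; one complication only |
| CPET v no-CPET comparison of predicted and actual outcomes | Not given |
| CPET measures against complications | AT ≤ 14 against collection only |

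The results text runs unbroken from cohort size to conclusion, so no redaction or missing figure accounts for the gaps.

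**2. The multivariate estimate**

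Inputs: ratio 3.5, 95% CI 1.6 to 657, p = 0.02. Assume a Wald interval, symmetric on the log scale.

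- Log limits: ln 1.6 = 0.470; ln 657 = 6.488.
- Centre: (0.470 + 6.488)/2 = 3.48; exp(3.48) ≈ 32.4.
- Standard error: (6.488 − 0.470)/(2 × 1.96) = 1.535.
- z = 3.479/1.535 = 2.27, two-sided p = 0.023. This reproduces the printed 0.02.
- With a ratio of 3.5 and the same standard error: ln 3.5 = 1.253, z = 1.253/1.535 = 0.82, p ≈ 0.41. This does not.
- Width: 657/1.6 ≈ 411-fold.

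The interval and the p-value agree with each other, and 3.5 fits neither as a ratio. It does match the log coefficient, 3.48. The label is a further mismatch: the only regression model named in the methods is binary logistic, which yields an odds ratio, and no time-to-event model is described.

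**3. How many people lie behind 60% v 9%**

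I listed every pair of groups totalling 30 or fewer in which a/n1 rounds to 60% and b/n2 rounds to 9%. The last four columns are p-values.

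| Counts | Total | Fisher | Chi-square | Yates | Wald |
|---|---|---|---|---|---|
| 3/5 v 1/11 | 16 | 0.063 | 0.029 | 0.120 | 0.052 |
| 6/10 v 1/11 | 21 | 0.024 | 0.013 | 0.045 | 0.028 |
| 9/15 v 1/11 | 26 | 0.014 | 0.008 | 0.026 | 0.021 |
| 3/5 v 2/22 | 27 | 0.030 | 0.008 | 0.045 | 0.021 |
| 3/5 v 2/23 | 28 | 0.027 | 0.007 | 0.038 | 0.019 |

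No fit totals 29 or 30, and truncating instead of rounding gives none there either. The 16-person table has no p-value that rounds to 0.02; each of the others has at least one. That leaves 21 to 28 people. If the percentages are collection rates by AT group, the collections number 7, 10, 5 and 5 in those four tables.

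**4. Multiplicity**

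The number of tests is not stated. Purely as an illustration, if AT ≤ 14 had been tested once against each of the nine complications, a Bonferroni adjustment would give 9 × 0.02 = 0.18. Trying other CPET measures or other cut-offs would add to the count.

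**The case against.** The AT analysis is within the plan's scope. The aim covers CPET parameters as predictors of morbidity. AT and intra-abdominal collection are both listed, and an analysis of CPET measures against complications is described. The Background cites a retrospective study showing that "CPET is useful to predict occurrence of post-operative pancreatic fistula, intra-abdominal abscess and post-operative length of hospital stay". The limitations concede the small CPET group. All of this stands, so a reader who infers that the AT result was an unplanned fishing exercise goes beyond the text. What remains is that planning a type of analysis does not fix the cut-off or say which complication leads, and a general remark about sample size neither labels this result exploratory nor says that the primary comparison went unreported.

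The results section is also only a short summary. The overview says in the past tense that the predicted-against-actual analyses were used. A reader might infer that the mortality analysis was abandoned or replaced because it was unfavourable; nothing in the document supports that.

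A reader might also infer from the three mortality bullets that the primary window is undefined. The lead sentence names 30 days. The role of the other two windows needs only a clarifying line.

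Finally, the printed percentages may themselves be inexact. The same paragraph gives 28.2% for 40 people, whereas 40/143 = 28.0% (40/142 = 28.2%), and 12/20 v 1/10 would give 60% v 10% in all 30. So a sample of fewer than 30 is conditional on correct printing, not established.

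**Conclusion.** The point holds as a reporting defect. The summary omits the stated primary and secondary comparisons and concludes, without an exploratory label, on one of nine complications at a cut-off absent from the methods. That part rests on the text alone and needs no assumption.

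The multivariate line is inconsistent as printed: its interval implies a ratio of about 32.4, not 3.5. That 3.5 is a log coefficient shown as a ratio is the likeliest explanation, given a Wald interval, but only the study output can confirm it. The 411-fold interval says little about the size of the association under either reading.

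The count of 21 to 28 people assumes correctly printed percentages and a p-value rounded from one of the four tests shown. The size of any mortality result cannot be judged, because the document gives no deaths or event rates. The conclusion should be made more cautious; it has not been shown to be false.

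**What to change.** 1. Report observed and predicted 30-day deaths by group and by score, with exact confidence limits, and note the imprecision expected in a group of 30. Present in-hospital and 90-day mortality as descriptive, and date this as a clarification made after the data were seen.
2. Report actual overall Clavien-Dindo grade 3 or higher morbidity against P-POSSUM-predicted morbidity. Compare it with CPET-predicted morbidity only if such a risk was recorded; if it was not, say so.
3. State in the conclusion whether the mortality question was answered. Label the AT ≤ 14 and collection result exploratory, and give its numerators and denominators, the origin of the cut-off and the number of CPET-measure-by-complication tests run.
4. Check the multivariate output and correct the ratio and its label so that they agree with the interval and the model fitted.

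The cost is one small table and some rewording, mostly from data the document says were collated; no new participants are needed. The CPET-predicted morbidity comparison may prove impossible, since the CPET list has one risk item with no event named. The downside is a more cautious conclusion, and the role given to the in-hospital and 90-day windows cannot be presented as pre-specified.
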